3.3.2 Missing Seizure/Medication Diary Entries

The calculation of seizure frequency endpoints will include only days for which diary entries are available. Missing seizure data will not be imputed.

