Patient rescreening is allowed as agreed by the sponsor and the investigator unless there is a general concern for patient safety or an inability for the patient to become eligible (e.g., GNX allergy, sensitivity or exposure, non-TSC and/or other ineligible epilepsy, chronic prohibited medical condition or treatment). Subsequent screening should take place at least 30 days from the patient's last visit, unless otherwise noted.

Part A includes a 4-week baseline and 4 weeks of IP titration followed by 8 weeks of dose maintenance followed by 2-week taper for those patients not continuing into the Part B OLE period. After meeting all eligibility criteria, approximately 30 patients aged 2 to 65 years (inclusive) with TSC-related epilepsy will be enrolled to receive GNX for a total of 12 weeks (4-week titration, 8-week maintenance) in addition to their standard anti-seizure medication(s) (ASMs). Patients will be titrated to 63 mg/kg/day (maximum 1800 mg/day) over 4 weeks, and then maintained at that dose for another 8 weeks. Patients who are not able to tolerate 63 mg/kg/day (or maximum 1800 mg/day) may be maintained on a lower dose after discussion with the sponsor medical monitor. A minimum dose of 33 mg/kg/day or 900 mg/day is generally required during the maintenance period.

For Part A, dose changes including alternative dosing paradigm (e.g., lower dose during the daytime and higher dose in the evening) should be discussed with the sponsor medical monitor

prior to making the change or within 48 hours of making the change. Patients who discontinue GNX should undergo a 2-week taper period, unless otherwise medically indicated. Patients who discontinue GNX before the completion of the maintenance period will continue to be followed per protocol and, at a minimum, patients will be encouraged to maintain daily seizure diaries until the maintenance period in Part A is completed. These patients will also return to the site 2 weeks after the taper for safety follow-up assessments.

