5. Have at least 8 countable/witnessed primary seizures during the 4-week baseline period with at least 1 primary seizure occurring in at least 3 of the 4 weeks of baseline. The primary seizure types are defined as the following: focal motor seizures without impairment of consciousness or awareness, focal seizures with impairment of consciousness or awareness, focal seizures evolving to bilateral, tonic-clonic convulsive seizures, and generalized motor seizures including tonic-clonic, bilateral tonic, bilateral clonic, or atonic/drop seizures. Focal aware non-motor and generalized seizures without motor features, infantile or epileptic spasms, and myoclonic seizures do not count as the primary seizure types.
6. Patient must be approved to participate by the sponsor or its designee (e.g., Epilepsy Consortium) after review of medical history, genetic testing, and patients' seizure types.

7. Patients should be on a stable regimen of ASMs at therapeutic doses for \geq 1 month prior to the screening visit, without a foreseeable change in dosing for the duration of Part A. Vagus nerve stimulator (VNS), ketogenic diet, and modified Atkins diet should be unchanged for 3 months prior to screening and will not count towards the number of ASMs.
8. Patients with surgically implanted VNS will be allowed to enter the study provided that all of the following conditions are met:
 - a. The VNS has been in place for \geq 1 year prior to the screening visit.
 - b. The settings must have remained constant for 3 months prior to the screening visit and remain constant throughout the baseline and Part A.
 - c. The battery is expected to last for the duration of baseline and Part A.
9. Parent/caregiver is able and willing to maintain an accurate and complete daily seizure diary for the duration of the study.
10. Able and willing to take IP (suspension) with food 3 times daily. (GNX must be administered with food).

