1.3.2 Sample Size Estimation

Approximately 36 TSC patients, aged 2 to 65 inclusive, will be screened to achieve 30 TSC patients given IP in Part A. Since this is an OL proof of concept study, sample size was not determined by statistical methods.

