2 STATISTICAL CONSIDERATIONS

2.1 GENERAL CONSIDERATIONS

Statistical analyses will be performed using SAS System, Version 9.4 or higher (SAS Institute, Inc., Cary, NC).

No formal hypothesis testing will be performed for this study. Data will be summarized descriptively. Separate summaries will be presented for data collected in Part A and data collected in Part B of the study. Unless otherwise specified, descriptive statistics for continuous variables will include number of non-missing observations (n), arithmetic mean, standard deviation (SD), 25th and 75th percentiles, minimum, median and maximum. For categorical variables, descriptive statistics including counts and percentages will be used. Only observed data will be summarized. Missing data will not

be imputed. Scheduled assessments will be included in summaries with the exception of reports of abnormal laboratory, vital sign, or ECG values.

Study data from all assessments (scheduled and unscheduled) will be displayed in individual data listings by study part (Part A or Part B), patient and visit, if applicable.

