2.2 ANALYSIS SETS

Analysis sets for this study are defined as:

- Screened population: all patients who have signed informed consent for the study.
- Safety population: all patients who have received at least one dose of GNX
- Intent-to-treat (ITT) population: all patients who receive at least one dose of GNX and have at least one post-baseline efficacy assessment.
- Per-protocol (PP) population: includes all ITT patients without major protocol violations, as will be defined prior to database lock. Patients that fall below 80% compliance at two consecutive visits during the maintenance period (i.e. Visits 4 and 5, Weeks 5 and 12) will not be included in the PP population.
- Open-label extension (OLE) population: includes all ITT patients who participate in the OLE (Part B) of the study and receive at least one dose of GNX in the Part B.
- Pharmacokinetic (PK) population: all ITT patients who have had at least one PK sample collected and a valid bioanalytical result obtained. Pharmacokinetic data collected from this population may be reported separately.

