3.1.3.2 Post-baseline seizure frequency – Maintenance Period, Part A, Part B and Overall

Post-baseline 28-day seizure frequency will be calculated as the total number of seizures in the specified post-baseline period divided by the number of days with non-missing seizure data in the same post-baseline period, multiplied by 28. Within Part A of the study, post-baseline seizure activity will be determined based on the days following the first day after the date of the first dose of IP. The first day of treatment is included in neither the baseline nor the post-baseline period since seizures reported on that date could have occurred either before or after the initiation of treatment. Within Part B (OLE

period), post-baseline seizure activity will be determined by the first day of OLE treatment.

Separate frequencies will be calculated for the 8-week maintenance period of Part A (Maintenance), Parts A (12-week treatment period consisting of a 4-week titration period and an 8-week maintenance period) and B of the study (OLE period of up to 24 weeks) and across both study parts.

Post-baseline specified study period 28-day seizure frequency =

$$\frac{\# \text{ seizures, specified study period}}{\# \text{ specified study period days with seizure data reported}} \times 28$$

3.1.3.3 Percent change in 28-day seizure frequency – Maintenance Period, Part A, Part B and Overall

% change from baseline =

$$\frac{[(\text{post-baseline 28-day seizure frequency}) - (\text{baseline 28-day seizure frequency})]}{(\text{baseline 28-day seizure frequency})} \times 100$$

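### With no minimum number of diary days, a patient who stops the diary after a few seizure-free days is counted as a ≥50% responder through Week 12

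*SAP*

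**What the plan says.** SAP 3.1.3.2 defines post-baseline frequency as seizures in the period "divided by the number of days with non-missing seizure data in the same post-baseline period, multiplied by 28". SAP 3.1.3.1 does the same for baseline. SAP 3.3.2 adds: "The calculation of seizure frequency endpoints will include only days for which diary entries are available", with no imputation. SAP 3.3 keeps early withdrawals in the analysis with whatever data they have. I found no minimum number of diary days in either document for baseline, for the treatment period or for responder status.

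The SAP's ITT set (2.2) is "all patients who receive at least one dose of GNX and have at least one post-baseline efficacy assessment", and Protocol 7.5 lists the daily diary among the efficacy assessments. The primary summary (SAP 4.2.1.1) uses all ITT patients and all available Part A seizure data. The ≥50% responder analysis (SAP 1.2.2.1 and 4.2.2.1) also uses ITT and has no completion or diary-day condition.

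The only sensitivity analysis (SAP 4.2.1.2) repeats the primary summary in the per-protocol set. The 80% rule for that set concerns study-drug compliance at two maintenance visits, not diary completeness. The other major violations are to be defined before database lock.

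On follow-up after stopping drug, Protocol 3.1 says "patients will be encouraged to maintain daily seizure diaries until the maintenance period in Part A is completed". Protocol 3.2 and 4.5.1 are firmer and say that diary recording continues. At entry, criterion 5 is a raw count: "Have at least 8 countable/witnessed primary seizures during the 4-week baseline period", with a seizure in at least 3 of the 4 weeks. Criterion 9 asks that the caregiver be able and willing to keep a complete diary.

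**The concern.** The responder endpoint is worded as a result through 12 weeks, but the formula lets one or a few days stand for all 84. A patient who leaves early, for intolerance for example, and whose few recorded days happen to be seizure-free is reported as a complete responder. Nothing in the planned analyses would show this in the responder percentage, because the per-protocol repeat covers only the primary summary and does not look at diary days.

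The study is single-arm and descriptive, so these percentages are its efficacy evidence. There is no control group in which the same artefact would also appear.

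The baseline has a related weakness. A seizure-free day enters the day count only if someone records it, so a diary kept mainly on seizure days would give too high a baseline frequency.

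**Working it through.** **Inputs.** There is no planned power, alpha or effect size to reproduce: "No formal hypothesis testing will be performed for this study" (SAP 2.1), and "sample size was not determined by statistical methods" (SAP 1.3.2). The denominator is the 30 treated patients of SAP 1.3.2. The frequency and percent-change formulas are those of SAP 3.1.3.1 to 3.1.3.3. The reference rate of 8 per 28 days is the entry minimum on a complete 28-day diary. My assumptions are Poisson counts, an unchanged rate (no drug effect) and a baseline known without error.

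**1. Score of a short seizure-free diary.** Frequency = 0 / d × 28 = 0, so the change is (0 − 8) / 8 × 100 = −100% for any d, whether 1, 3, 7 or 14 days. The patient is a ≥50% responder.

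**2. Chance of a false ≥50% response.** With d diary days the mean count is m = (rate / 28) × d. The patient is a responder if the count is at most m / 2. The last row gives the chance of no seizure at all in 3 days, exp(−m).

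| Diary days | 8 per 28 | 12 per 28 | 20 per 28 | 40 per 28 |
|---|---|---|---|---|
| 1 | 75% | 65% | 49% | 24% |
| 3 | 42% | 28% | 37% | 20% |
| 7 | 41% | 20% | 12% | 7% |
| 28 | 10% | 5% | 1% | 0.04% |
| 84 | 0.5% | 0.07% | <0.01% | <0.01% |
| Zero seizures in 3 days | 42% | 28% | 12% | 1.4% |

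The columns and rows are not perfectly smooth because counts are whole numbers. For example, at 8 per 28 with 3 days only a count of 0 qualifies, while with 7 days (m = 2) a count of 0 or 1 does.

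**3. Effect on the responder percentage.** Each false responder adds 1 / 30 = 3.3 points, and three add 10. As an illustration with assumed counts, take 9 true responders plus 3 patients with short seizure-free diaries:
- SAP rule: 12/30 = 40.0% (95% CI 22.7 to 59.4).
- Short diaries as non-responders: 9/30 = 30.0% (14.7 to 49.4).
- Short diaries excluded: 9/27 = 33.3%.

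**4. Effect on the primary mean.** The expected count is (rate / 28) × d, so the expected frequency is the true rate for any d, and the expected change is 0. With 3 days at 8 per 28, 42% of patients score −100% and the other 58% score +17% or more. One seizure gives 1 / 3 × 28 = 9.3, or +17%; three give 28, or +250%. Short diaries therefore add variance in both directions.

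**5. Baseline.** If all unrecorded days of a 28-day baseline were seizure-free and the treatment diary is complete, an unchanged patient scores d / 28 − 1:
- 20 recorded days: −29%
- 14 recorded days: −50%
- 8 recorded days: −71% (8 seizures give 28 per 28)

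If days are missing at random, the formula itself gives no inflation: the expected frequency stays at 8. The raw entry count still selects upward near the threshold. At a true 12 per 28, mean baseline among eligible patients is 12.6 with 28 recorded days, 14.5 with 20 and 18.5 with 14. At 40 per 28 there is no such effect.

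**The case against.** **Short diaries may be rare.** The patient must abandon the diary, not only the drug. Protocol 3.2 and 4.5.1 expect recording to continue, and patients who stop normally taper for 2 weeks and return 2 weeks later with a diary review. SAP 3.2 counts taper and safety visits in the 12-week period for those not continuing. Entries are expected within 48 hours and monitors review all of them (Protocol 9.1); caregivers are re-educated as needed (6.5). This stands as to likelihood: neither document gives a dropout or completeness figure, so short diaries cannot be called likely. It does not supply an analysis rule for when follow-up fails.

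**The size depends on the rate and on the days recorded.** This also stands. Three dropouts with 7 diary days each at 8 per 28 yield on average 3 × 0.41 = 1.2 false responders, or 4 points rather than 10.

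**A reader might infer that both gaps favour the drug throughout.** The documents do not support that. For the primary mean the expected shift is zero (step 4). An incomplete baseline inflates only if seizure-free days are selectively unrecorded, or near the 8-seizure threshold; unrecorded seizure days would deflate it. The −71% case needs 20 of 28 days blank, despite a daily yes/no diary question (SAP 3.1.3.4) and a diary review before dosing at Visit 2.

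**A reader might also infer that completeness improves on treatment,** since no diary contact is scheduled between Visits 1 and 2 and eight follow dosing by Week 5. That is conjecture; the documents contain nothing to test it.

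**Consequences are bounded.** No test is affected, patient listings are planned, and the 35% extension criterion can be waived with sponsor approval. True, but the responder percentage will still be read as a headline figure.

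**Conclusion.** The concern holds for the ≥50% responder percentage. By the SAP's own formulas, a patient with only a few seizure-free post-baseline days is a complete responder through Week 12, and no planned analysis corrects this. Among patients whose seizures have not changed, the error can only add responders, because a short diary with many seizures leaves the patient a non-responder. The chance is about 42% with 3 diary days and 41% with 7 at the entry rate, against 0.5% over 84 days, and each case adds 3.3 points among 30. These figures rest on Poisson counts, a constant rate and a known baseline.

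For the primary mean the problem is added noise, not expected bias. For baseline, inflation is conditional on selective recording or on a rate near the entry count. If it occurs, artefacts of −50% or −71% would also pass the 35% extension criterion. How many patients would be affected cannot be derived from the documents.

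**What to change.** 1. **SAP 4.2.2.1.** Count a patient as a ≥50% responder only with at least 28 post-baseline Part A diary days. ITT patients with fewer stay in the denominator as non-responders. Show the all-available-data responder rate alongside, since the rule can also misclassify a true responder with a short diary.
2. **SAP 4.2.1.2.** Add a sensitivity summary of the primary endpoint in patients with at least 28 post-baseline and at least 24 baseline diary days. Label it supportive, because the restriction itself selects patients, including out those with large increases. Report the number of diary days per patient in each period.

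With 28 days the false-response chance at the entry rate falls to about 10%. With 24 of 28 baseline days, the selective-recording artefact is at most 24 / 28 − 1 = −14%, short of both the 35% and 50% thresholds.

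The cost is one SAP rule, one extra table and possibly a slightly lower responder percentage. The 28- and 24-day cut-offs are conventions, not derived values, and must be fixed before database lock. While SAP 4.2.2.1 is open, its reference for percent reduction should point to 3.1.3.3; it now points to 3.1.3.6, which concerns seizure-free days.

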4 STATISTICAL ANALYSES

4.1 SUBJECT INFORMATION

4.1.1 Disposition of Subjects

The number of patients screened for this study, the number of screen failures and the number of patients who received at least one dose of IP in each part of the study (Part A and Part B) will be summarized. Reasons for screen failure will be provided in the data listing.

The final disposition of all patients who receive IP will be summarized by study part (Part A and Part B). Reasons for discontinuation of study treatment and for discontinuation of study participation will be summarized. The total number and percentage of patients who complete Part A of the study will be summarized as will the number and percentage of these patients who continue participation in Part B of the study. In addition, the number and percentage of patients who complete Part B of the study will be summarized

separately.

A listing of patient disposition will be provided.

In addition, a summary of the number of patients included in each analysis set will be presented.

4.1.2 Protocol Violations

Protocol violations will be identified prior to database lock. Protocol violations will be listed for patients in the Safety Population.

4.1.3 Demographics and Baseline Characteristics

Demographics and baseline characteristics will be summarized and listed for all patients in the Safety Population participating in Part A of the study and OLE patients participating in Part B of the study. Demographic characteristics, including age, height, weight and BMI, will be summarized with descriptive statistics (n, mean, median, SD, minimum and maximum). Categorical characteristics such as age group (≤ 17 years, > 17 years), weight group (≤ 28 kg, > 28 kg), sex, race and ethnicity, will be summarized as counts and percentages.

Additionally, baseline clinical characteristics including results of genetic testing for pathogenic or likely pathogenic TSC1 or TSC2 variant, Tanner Staging, number of AEDs taken and stopped prior to screening, neurological exam results, developmental examination results (pediatric patients aged 2 to 17, inclusive), and Seizure Identification and Diagnostic Review Form (SIF/DRF) responses including baseline seizure types reported as primary and non-primary, IQ, intellectual disabilities, and [REDACTED].

Baseline values of efficacy and safety parameters will be summarized in the respective analysis tables.

4.1.4 Medical History

Medical history will be coded using Medical Dictionary for Regulatory Activities (MedDRA), version 22.0. The number and percent of subjects with clinically significant medical history at screening will be summarized by system organ class (SOC) and preferred term (PT) in the Safety population. Medical history will also be listed.

4.1.5 Prior and Concomitant Medications

All investigator terms for medications recorded on the CRF will be coded using the World Health Organization Drug Dictionary Enhanced (WHODDE) Anatomical Therapeutic Chemical (ATC) drug dictionary (Version WHODDE, September 2019). The number (percentage) of subjects who took prior and concomitant medications will be summarized in the Safety population by Anatomic Therapeutic Chemical (ATC) classification level 2 and Preferred Term (PT). September 2019.

Prior medications are defined as medications that started prior to the first dose of study drug. Concomitant medications are defined as medications (other than the study drug)

taken on or after the first dose of the study drug. Medications started before the first dose of study drug and continuing at the time of the first dose of study drug are considered both prior medication and concomitant medication. The summary of concomitant medications for Part A of the study will not include concomitant medications that start after Part A; i.e., they will not include any concomitant medications starting on or after the first dosing day of the OLE phase.

The number and percentage of patients in the Safety population reporting use of prior and concomitant treatments will be summarized and listed separately. In addition, antiepileptic prior and concomitant drugs (AEDs) and rescue medications will be presented separately. Prior medications will be summarized for Part A only. All other summaries and listings will be presented separately for Parts A and B of the study.

4.1.6 Treatment Compliance

Compliance with GNX treatment will be assessed by inspecting the seizure and medication diary entries and returned drug supply with queries as necessary. Treatment compliance will be calculated as explained in Section 3.1.3.7. Percent compliance for Parts A and B of the study will be summarized for the Safety Population and OLE Population, respectively. Reported dosing by visit and calculated compliance values will be listed.

4.2 EFFICACY ANALYSES

4.2.1 Primary Efficacy Analysis

4.2.1.1 Primary Analysis

The primary efficacy endpoints, the percent change in 28-day primary seizure type frequency through the end of the 12-week treatment period (Part A; 4-week titration and 8-week maintenance) relative to the baseline, is defined in Section 1.2.1. The calculation of the primary endpoint is described in Section 3.1.3.

Descriptive summaries including the number of patients with non-missing primary seizure data, mean arithmetic change and percent change in 28-day primary seizure type frequency from baseline and associated 95% confidence intervals, SD, minimum, median and maximum values will be presented for the baseline period, 4-week titration period, 8-week maintenance period and 12-week treatment period. All patients in the ITT population and all available seizure data within Part A of the study will be included in these analyses regardless of whether the patient stopped taking IP or took rescue medication.

Additionally, a by-patient listing of seizure data collected during Part A will be provided.

4.2.1.2 Sensitivity Analysis

The primary analysis will be repeated in the PP population.

4.2.2 Secondary Efficacy Analysis

Secondary efficacy endpoints are defined in Section 1.2.2. Analyses of secondary

efficacy endpoints will be based on the ITT population.

